**Study Protocol**

**20th February 2018**  
**(Version 1.0)**

**Sponsor:** AIFA (Agenzia Italiana del Farmaco) and Ministry of Health

**Principal Investigator:** [name]

**Coordinating Committee:** Institute of Neurology, Catholic University of The Sacred Heart, Rome, (Responsible: [name]); IRCCS Centro San Giovanni di Dio Fatebenefratelli, Brescia (Responsible: [name]); IRCCS Foundation "Carlo Besta" Neurological Institute, Milan (Responsible: [name]); National Institute of Health (Responsible: [name]); Associazione Italiana Malattia Alzheimer - AIMA (Responsible: [name]); Istituto Nazionale Ricovero e Cura Anziani – IRCCS-INRCA (Responsible: [name]).

**Study classification:** This is an interventional non therapeutic clinical trial. It is a diagnostic trial which is aimed at finding new ways for early detection and diagnosis of medical conditions.

**Biomarkers included in the study:** MMSE; FCSRT; CSFp-tau and CSF p-tau/ABeta; (F)FDG-PET SCAN; Volumetric MRI; ApoE4; EEG.

**Design:** multicenter, interventional cohort study.

**Number of patients in the study:** 400.

**Number of participating Recruiting Centres:** 20 centres (identified following a public call by AIFA).

**Number of Expert Centres:** 4 (Institute of Neurology, Catholic University of The Sacred Heart for EEG; IRCCS Centro San Giovanni di Dio Fatebenefratelli for neuropsychological tests and volumetric MRI; IRCCS Foundation "Carlo Besta" Neurological Institute for liquoral markers and APOE4; IRCCS, Nuclear Medicine, San Raffaele Hospital, Milan for PET).

**Funding:** AIFA and Ministry of Health

## LIST OF ABBREVIATIONS

A-beta42= Beta amyloid peptide of 42 aminoacids

AD= Alzheimer's Disease

AES= Advanced Encryption Standard it is a specification for the encryption of electronic data established by the U.S. National Institute of Standards and Technology

AIFA= Agenzia Italiana del farmaco; Italian Medicines Agency

aMCI= amnesic Mild Cognitive Impairment

ApoE= Apolipoprotein E

AEs= Adverse Events

BA= Brodmann Areas (histologic classification of cortical brain areas)

CDCD= Centro Disturbi Cognitivi e Demenza; Center for Cognitive Disorders and Dementia

CDR= Clinical Dementia Rating scale

CDMS= Clinical Data Management System

CC= Coordinating Committee

CRF= Case Report Form

CSF= Cerebro-SpinalFluid

DFR= Delayed Free Recall (neuropsychological test)

DTI= Diffusor Tension Imaging (method of MRI analysis for fiber tracts)

EC= Expert Centre

EDTA= Etilen DiamminoTetraacetic Acid

EEG= Electroencephalogram

EOAD= Early Onset Alzheimer's Disease

FCSRT= Free & Cued Selective Reminding Test

(F) FDG= (F) Fludeoxyglucose (radionuclide for PET)

FTP= Full Time Person

GANTT (diagram)= instrument for project management in memory of Henry L. Gantt

GCP= Good Clinical Practice

HIV= Human Immunodeficiency Virus

HTLM= HyperText Markup Language; it is the language to create web pages and other documents visible on a browser

Hz= Hertz (cycles/sec)

ICA= Independent component Analysis

INRCA= Istituto Nazionale Ricovero e Cura Anziani; National Institute for Hospitalization and Elderly Care

IRB= Institutional Review Board

IRCCS= Istituti di Ricovero e Cura a Carattere Scientifico; Scientific Institutes for Hospitalization and Care

IWG2= International Working Group (on Alzheimer diagnostic criteria)

LORETA= Low Resolution brain Electromagnetic Tomography

NPT= Neuro Psychological Tests

MCI= Mild cognitive Impairment

MMSE= Mini Mental State Examination

MRI= Magnetic Resonance Imaging

NIA-AA= National Institute on Aging - Alzheimer Association

PET= Positron Emission Tomography

RC= Recruiting Centre

RCT= Randomized Controlled Trial

ROI= Region of Interest

SIN-Dem= Società Italiana Neurologia - gruppo di studio Demenze; Italian Society of Neurology - Working Group on dementia

SPSS= Statistical Package for Social Science

STARD= Standards for Reporting Diagnostic Accuracy (statement developed in order to improve the standards for reporting of studies on diagnostic accuracy)

1.5-3T= 1.5-3 Tesla (intensity of the MRI magnetic field)

## SYNOPSIS

In the next 8 years a number of phase 2-3 trials will end up which utilize experimental drugs possibly *disease modifying* for Alzheimer Dementia. They target different disease stages: mild-moderate AD, 'early' AD, MCI prodromic to AD (MCI + for biomarkers heralding progression to AD), pre-symptomatic AD in pathogenetic gene mutation carriers of familiar AD forms. This dense clinical trials activity has triggered a fundamental question both from Patients and Scientific Communities and Health Authorities/Insurances: on which basis will the new drugs –if effective– be distributed to patients or at-risk population? This question mainly deals with the “MCI prodromal to AD” condition since the MCI population actually includes about 50% of those who will progress to AD (the real “prodromic to AD” MCI form) while the remaining 50% will never convert to AD. Since the new drugs –if effective– will carry both elevated unit costs and not marginal side-effects, they should be administered selectively to those MCI with a severely high risk of conversion (i.e. 90% or more) and particularly to those with a high risk of rapid conversion (1-2 years from diagnosis of the MCI condition).

The INTERCEPTOR project is focused on the prodromic AD condition (IWG2) or the MCI condition (NIA-AA) which form the neuropsychological point of view and is characterized by means of: cognitive questionnaire, screening test (MMSE), extended neuropsychological evaluation (incl. 2 episodic memory tests, language test, visuo-spatial abilities evaluation, behavioural scales Costa et al, 2017; Cerami et al, 2017), functional scales (Annex), full neurological examination. CDR must be 0.5. Atypical types of clinical presentations must be particularly considered (i.e. non amnesic debut) for a differential diagnosis where the role of biomarkers is pivotal.

In Italy, according to a recent study (Cohort Studies Memory in an International Consortium-COSMIC), an MCI prevalence of 5.9% has been evaluated in over 60 yrs population, with an increase of 4.5% between 60 & 69 yrs, of 5.8% between 70 & 79 yrs, and up to 7.1% in the 80 - 89 yrs range. On this epidemiological basis about 735.000 MCI cases are estimated for 2016 in the resident Italian population .

### **Study design and methods**

Multicentric non therapeutic cohort study in subjects fulfilling the MCI “core” criteria as defined by the National Institute on Aging-Alzheimer’s Association workgroups on diagnostic guidelines for Alzheimer’s disease (Albert et al., 2010). The study design reflect a longitudinal cohort study in which the baseline clinical and biomarkers characteristics of the enrolled MCI subjects at baseline will be compared for those classified as “AD converters” after 3.0 years of follow-up with respect to those “non converters”. MCI subjects who will convert to other forms of dementia will be examined separately.

Number of MCI to enroll about 480 with a target of 400 full evaluated having about 20% of dropout. Total duration of the study 54 months.

All the medications at baseline are allowed without modifications for the whole protocol except for urgencies.

Neuropsychological follow-up tests will be carried out at 6 months intervals (total 7 from T0= baseline to T6= 42 months).

Within 60 days from T0 biomarkers must be carried out/collected including:

MMSE & DRF – FCSRT)  
DNA extraction and ApoE typing  
Lumbar Puncture for Beta/Tau metabolites  
EEG for brain connectivity with graph theory  
MRI + hippocampal volumetry  
(F)FDG-PET

## **Endpoints**

### **Primary Endpoint**

It will be considered the conversion to Alzheimer's disease within 3.0 years after diagnosis of MCI, together with the assessment of those who remain in a stable condition and those who have a reversion to normal cognitive profile. People with MCI who convert to other forms of dementia will be considered separately. The biomarker or a set of biomarkers that can predict the conversion to Alzheimer's disease with higher accuracy will be evaluated.

### **Secondary Endpoints**

Evaluation of cost/benefit ratio of individual and combination of biomarkers compared to their accuracy to predict progression from MCI to AD and their financial sustainability, availability in the country and non-invasiveness for patients.

### **Inclusion criteria:**

- a) age between 50 and 85 years;
- b) age and education corrected Mini Mental State Examination score equal or superior to 24/30;
- c) Clinical Dementia Rating (CDR) global score of 0.5;
- d) concerns about cognitive modifications, expressed as subjective complaints by the subject, or by impression by a close acquaintance or an expert clinician;
- e) defective performance with reference to age and education matched controls in one cognitive domain (memory, executive function, attention, language, visuospatial function): if repeated assessments are available, evidence of performance decline;
- f) preserved functional autonomy: the subject remains fully independent, even if specific performances may be slower, less efficient than usual level, with occasional errors;
- g) no dementia: the cognitive modifications do not significantly hamper social function or work activities.

### **Exclusion criteria:**

- a) history of cerebrovascular disease (i.e. stroke episodes), alcohol abuse, severe medical disorders associated with cognitive impairment (organ failures, endocrine disorders, in particular thyroid disease and B12/folates deficiency); neuroimaging evidence of other potential causes of cognitive decline (e.g. subdural haematoma, malignancy etc.); chronic treatment with psychotropic drugs; women in reproductive age;
- b) history of malignancy < 5 years;
- c) contraindications for Magnetic Resonance Imaging (MRI): pacemaker; spinal stimulators; defibrillator; any other condition incompatible with MRI acquisition;
- d) presence of spinal malformations or any other contraindications to lumbar puncture, according to the investigator's judgement;
- e) HIV infection;

- f) use of drugs potentially affecting cognitive function, according to the investigator's judgement;
- g) subjects are not allowed to participate in any trial with experimental drug;

**Exclusion criteria specific to lumbar puncture:**

Patients who refuse to or cannot temporarily interrupt antiplatelet or anticoagulant therapy 14 days prior to sampling visit.

# 1. INTRODUCTION

## 1.1 The 3 main scenarios

There is a tremendous impetus in clinical research in the attempt of finding out a disease-modifying therapy for the various forms of dementia, namely of the Alzheimer's type dementia (Alzheimer's disease = AD). Below an outline of the 3 most frequent scenarios in daily clinical practice, which represent the respective targets for experimental therapies aiming to interfere with the natural course of the disease either blocking or slowing down its progression.

Scenario 1 - Asymptomatic subjects at high risk; this definition is presently applicable to overall healthy subjects carrying genetic mutations which are pathogenic for AD or FTD (guidelines for detailed description of high-risk subjects are fully described in SINDEM consensus paper by Bocchetta et al. 2016). The asymptomatic stage must be verified by means of a dedicated questionnaire for cognitive symptoms, of an accurate neuropsychological evaluation and a full neurological examination. The Clinical Dementia Rating scale (CDR) must be 0. In the case of familial history of dementia, a genetic counselling and testing shall be performed together with an accurate analysis of the age of onset of symptoms with the aim of establishing in advance the age for starting therapy. If the family carries pathogenic mutations, the use of biomarkers is considered useful just for follow-up, but not for diagnostic purposes. It is estimated that early onset AD cases (EOAD) represent 35 per 100.000 inhabitants between 45-64 years of age (Stevens JC et al. 2011). With this value in mind, it can be assumed that in Italy there are presently (2016) about 6000 cases with EOAD, about 50% of which carries mutations of the pathogenic genes.

Scenario 2 – the one to which the present research protocol is targeted- Subjects with a prodromal stage of AD (IWG2) or Mild cognitive impairment (MCI) prodromic to AD (NIA-AA). MCI is a clinical and neuropsychological state in the elderly brain – an intermediate stage between normal cognition and dementia. It is mainly characterized by objective evidence of memory impairment during a neuropsychological examination which does not yet fulfill the definition of dementia. Epidemiological research suggests that amnesic MCI (aMCI) is a precursor to Alzheimer's Disease (AD), based on the high rate of progression from this state to AD. Between 50 and 60% of MCI subjects convert to dementia. The remaining individuals will either stay in the MCI condition or return to a fully normal one and never progress to dementia. In order to plan optimal and early therapeutic, organizational and rehabilitative interventions, aMCI diagnosis should be combined

with the most reliable prognosis on the likelihood and time of progression to dementia. The MCI definition requires the following: cognitive questionnaire, screening tests (MMSE), neuropsychological evaluation (including 2 tests for episodic memory, tests for language, visuo-spatial abilities and behavioural scales with appropriate normative thresholds; Costa et al. 2017; Cerami et al. 2017), functional scales, neurological examination and a CDR score of 0.5. Growing evidence suggests that early diagnosis reduces health and social costs for dementia management. Moreover, and strictly related to this research protocol, MCI prodromal to AD is becoming increasingly frequent and is the preferred target for clinical trials with potential disease-modifying experimental drugs. Early diagnosis of the MCI condition prodromal to AD can presently be achieved with a very high sensitivity and specificity by combining a number of tests (i.e. hippocampal volumetric MRI, (F)FDG-PET and lumbar puncture for CSF examination). However, due to their elevated costs, low availability and/or invasiveness, these cannot be applied to evaluate a large population sample -for instance on a national scale-. In a recent study by an international consortium (Cohort Studies Memory in an International Consortium-COSMIC - Sachdev PS et al., 2015) it was attempted to define the epidemiological boundaries of the MCI condition through a meta-analysis of the published data. A prevalence of 5.9% has been estimated in population with >60 years, with an increment of the stratified age ranges from 4.5% (60 to 69 years), to 5.8% (70 to 79 years) and 7.1% (80 to 89 years). Based on such values, around 735.000 MCI subjects are estimated in the Italian population as of 2016. As aforementioned, the motivation of focusing the present research project on this type of subjects (scenario 2) relies on the growing evidence that the prodromic stage seems the most responsive to experimental disease modifying drugs (including some of those which have recently failed in the early/moderate AD stage).

Scenario 3- Patients with early AD condition which is defined by means of the following: cognitive questionnaire, screening tests (MMSE after correction for age and education, score between 21 and 25/30), neuropsychological evaluation (including 2 tests for episodic memory, tests for language, visuo-spatial abilities and behavioural scales with appropriate normative thresholds; Costa et al. 2017; Cerami et al. 2017), functional scales, neurological examination and a CDR score of 1. Epidemiological evidence indicate that in Italy there are presently about 500.000 AD cases. Although it is not easy to evaluate how many of them are in the early stage, by taking advantage of previous attempts from the CRONOS project, it can be predicted that about 60% of them – nearly 300.000 patients- are currently in an ‘early’ stage of disease (Vanacore et al. 2004).

## 1.2 Biomarkers role

The role of biomarkers in the diagnosis of dementia is becoming all the more important as the need for an 'early' diagnosis is now prominent, namely a diagnosis in pauci- or asymptomatic disease stages. Three separate research strings have been launched on PUBMED:

A) (biomarker\* OR "blood" OR "serum" OR "plasma" OR "cerebrospinal" OR "cerebro-spinal" OR "csf" OR liquor\* OR biops\* OR bioptic\* OR urine\* OR saliva OR neuroimag\* OR neuro-imag\* OR imaging) AND ("mild neurocognitive disorder" OR "minor neurocognitive disorder" OR "mild cognitive impairment" OR "MCI") AND (predictive\* OR prediction\*) AND (progression OR conversion).

B) (biomarker\* OR "blood" OR "serum" OR "plasma" OR "cerebrospinal" OR "cerebro-spinal" OR "csf" OR liquor\* OR biops\* OR bioptic\* OR urine\* OR saliva OR neuroimag\* OR neuro-imag\* OR imaging) AND ("major neurocognitive disorder" OR "mild neurocognitive disorder" OR "minor neurocognitive disorder" OR "mild cognitive impairment" OR "MCI" OR Alzheimer\*) AND (diagnosis OR diagnostic\*).

C) (\*encephalography\* OREEG ) AND (alzheimer\* OR "mild cognitive impairment") AND ("diagnosis" OR "diagnostic" OR "progression" OR "conversion").

The main criterion for quality selection was focussed on those biomarkers which best predict progression from MCI to AD in longitudinal studies, while cross-sectional studies were excluded. If in the review a 'pooled' estimate was not available, the study with the larger sample was selected in order to obtain a more careful estimate with a small 95% CI. When considering the best evidence for each biomarker, Cochrane reviews were preferred (whenever available) which identify quality of the studies by means of the checklist QUADAS (Quality Assessment of Diagnostic Accuracy Studies) and STARD (Standards for Reporting Diagnostic Accuracy). Only for EEG a single study was taken into account.

Below is the best scientific evidence on the *sensitivity* and *specificity* parameters for individual biomarkers identified with a 95% CI threshold in case 400, 600 or 800 MCI subjects are enrolled.

### Biomarker 1: Mini-Mental State Examination

Cochrane review title: "Mini-Mental State Examination (MMSE) for the detection of Alzheimer's disease and other dementias in people with mild cognitive impairment (MCI) (Arevalo-Rodriguez

et al. 2015)". The authors' conclusions underline a "limited investigation of heterogeneity due to insufficient number of studies".

The pooled estimate is not present, therefore it was considered the study of Xu G., et al., 2002 performed on 351 patients with MCI.

	Xu 2002 (n=351)	n=400	n=600	n=800
Sensitivity (CI95%)	0.57 (0.46; 0.68)	0.57 (0.46; 0.68)	0.57 (0.48; 0.65)	0.57 (0.50; 0.64)
Specificity (CI95%)	0.86 (0.81; 0.90)	0.86 (0.81; 0.90)	0.86 (0.82; 0.89)	0.86 (0.83; 0.88)

**Biomarker 3: Cerebro-Spinal-Fluid (CSF) p-tau e ratio tau/ABeta**

Cochrane review title: "CSF tau and the CSF tau/ABeta ratio for the diagnosis of Alzheimer's disease dementia and other dementias in people with mild cognitive impairment (MCI) (Ritchie c., et al., 2017)". The authors' conclusions underline a "limited investigation of heterogeneity due to insufficient number of studies. Lack of common thresholds "

The "pooled" estimate is missing; therefore, it was considered the study of Vos SJ. et al. 2013 performed on 214 patients with MCI.

	Vos 2013 (n=214)	n=400	n=600	n=800
Sensitivity	0.71 (0.61; 0.80)	0.71 (0.64; 0.78)	0.71 (0.65; 0.77)	0.71 (0.66; 0.76)

(CI95%)				
Specificity (CI95%)	0.77 (0.69; 0.84)	0.77 (0.71; 0.83)	0.77 (0.72; 0.82)	0.77 (0.73; 0.81)

**Biomarker 4: (F)FDG-PET**

Cochrane review title: “F-FDG PET for the early diagnosis of Alzheimer's disease dementia and other dementias in people with mild cognitive impairment (MCI) (Smailagic N. et al. 2015)”. The authors' conclusions underline a "Limited investigation of heterogeneity due to insufficient number of studies. Lack of common thresholds". The pooled estimate is not present, therefore it was considered the study of Herholz K. et al, 2011, performed on 94 patients with MCI.

	Herholz2011 (n=94)	n=400	n=600	n=800
Sensitivity (CI95%)	0.57 (0.37; 0.75)	0.57 (0.48; 0.65)	0.57 (0.49; 0.64)	0.57 (0.50; 0.63)
Specificity (CI95%)	0.67 (0.54; 0.78)	0.67 (0.61; 0.73)	0.67 (0.62; 0.72)	0.67 (0.63; 0.71)

**Biomarker 5: at least the presence of one allele APOE ε 4**

Title meta-analysis of four prospective studies: “Apolipoprotein 4 allele ε4-as a significant risk factor for conversion from mild cognitive impairment to Alzheimer's disease: a meta-analysis of prospective studies (n = 458) (Fei M. et al. 2013)”.

	Fei 2013 n=458	n=400	n=600	n=800
Sensitivity (CI95%)	0.52 (0.45; 0.60)	0.52 (0.44; 0.60)	0.52 (0.46; 0.59)	0.52 (0.47; 0.58)
Specificity (CI95%)	0.66 (0.59; 0.71)	0.66 (0.59; 0.71)	0.66 (0.60; 0.70)	0.66 (0.61; 0.70)

Biomarker 6: multiple six electroencephalogram (EEG) biomarkers into a diagnostic classification index

It was identified the following study "Integrative EEG biomarkers predict progression to Alzheimer's disease at the MCI stage." (Poil SS et al., 2013), which shows interesting values of sensitivity and specificity of the EEG via modern methods of analysis.

	Poil n=30	n=400	n=600	n=800
Sensitivity (CI95%)	0.87 (0.47; 1.00)	0.87 (0.80; 0.93)	0.87 (0.81; 0.92)	0.87 (0.82; 0.91)
Specificity (CI95%)	0.64 (0.41; 0.83)	0.64 (0.58; 0.69)	0.64 (0.59; 0.68)	0.64 (0.60; 0.68)

Biomarker 7: volumetric MRI

Title pooled analysis: "Imaging markers for Alzheimer's disease: which vs how. Neurology 2013; 81:487-500, (Frisoni G.B. et al., 2013)".

	Frisoni 2013 (n=416)	n=400	n=600	n=800
Sensitivity (CI95%)	0.60 (0.51; 0.68)	0.60 (0.51; 0.68)	0.60 (0.54; 0.66)	0.60 (0.55; 0.65)
Specificity (CI95%)	0.75 (0.67; 0.82)	0.75 (0.67; 0.82)	0.75 (0.70; 0.79)	0.75 (0.71; 0.79)

**The present study protocol is focused on the second scenario and therefore includes the definition of prodromal AD (IWG2) or MCI (NIA-AA).**

## **2. OBJECTIVES OF THE STUDY**

Whereas scientific literature is always more abundant in contributions to the profiles of individual sensitivity and specificity biomarkers, much fewer studies have evaluated combinations of multiple markers on the same study population. Furthermore, to date no study has assessed and validated an organization model for screening large part of the population using combinations of biomarkers, in terms of feasibility of costs, distribution and operational feasibility. Indeed these are the key points that this Protocol seeks to address.

The primary aim is to identify a biomarker or a set of biomarkers able to predict with greater accuracy the conversion of MCI to Alzheimer's dementia after 2 or 3 years of follow-up. The secondary aim is to define an optimal organizational model, as regards transferability in clinical practice of the defined diagnostic path of the primary objective as well as sustainability costs, in order to identify patients eligible to prescription of antidementia drugs which are currently under experimentation by RCTs.

### **3. METHODS-STUDY DESIGN**

#### **3.1 Overall design**

Multicentric interventional non therapeutic cohort study on a sample of 400 subjects consecutively diagnosed with MCI at the Center for Cognitive Disorders and Dementia (the Italian acronym is CDCD). The subjects shall fulfill the “core” criteria for MCI as defined by the *National Institute on Aging-Alzheimer’s Association workgroups on diagnostic guidelines for Alzheimer’s disease* (Albert et al., 2011).

The MCI sample shall be recruited in the cohort study, with the aim of comparing the baseline characteristics (clinical and biomarkers) between the group progressing to AD after 2 and 3 years from diagnosis and the group remaining stable or reverting to a normal condition. The recruited MCI subjects progressing to a non-AD dementia shall be considered separately.

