### 3.7 Endpoints

#### Primary Endpoint

It shall be considered the conversion to Alzheimer's disease within 3.0 years after diagnosis of MCI, together with the assessment of the subjects remaining in a stable condition and of those showing a reversion to the normal cognitive profile. People with MCI who convert to other forms of dementia will be considered separately. The biomarker or a set of biomarkers will be evaluated which can predict the conversion to Alzheimer's disease with higher accuracy.

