**Table 5. EEGSample size dimensions for a case-control unpaired study**

For:	Level of bilateral confidence (1-alpha)	99.9	
	Potency (% possibility of identification )	99	
	Ratio controls-cases	2	
	Hypothetical proprtion of controls with exposure	36.4	
	Hypothetical proprtion of cases with exposure:	87.5	
	Odds Ratio minimo estremo da rilevare:	12.23	
	Kelsey	Fleiss	Fleiss con CC
Sample size – Cases	46	38	41
Sample size - Controls	91	75	81
Sample Size- total sample:	137	113	122

It is not possible to apply an estimate of sample size to a pair of biomarkers as there are no specific data in the literature for the 2 couples with the highest sensitivity values previously reported (table 1). It should be noted that -as will be reported in the next paragraph- it is necessary to capture the full data set in order to have the number of cases which convert and do not convert to Alzheimer’s dementia for each of the 4 combinations of a biomarker pair (++; +-;+;- -). On the basis of relevant literature, using two specific approaches for sample size calculation for a single biomarker and estimating an approximate 20% drop-out rate for various reasons (death, severe neurodegenerative disease, dropout for poor compliance) during the follow up, a sample size of 400 patients with MCI is considered sufficient to highlight a biomarker or a pair of biomarkers with such a level of accuracy as to trigger the decision to prescribe a new anti-dementia medicinal product.

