### 3.10 Statistical Analysis

Statistical analysis will be carried out following three areas:

1. Preparation of contingency tables for each of the seven biomarkers (MMSE; FCSRT; CSF CSF tau and p-tau/ABeta; F)FDG-PET; ApoE4; EEG) and processing parameters of sensitivity, specificity, positive predictive value and negative predictive value and overall accuracy. We will also calculate the positive and negative likelihood ratios (LR). The related 95% CI for each of these parameters shall also be calculated. The results will be compared with the positive and negative LR values, which are considered the gold standard for the placing on the market of a diagnostic test. (Jaeschke R, Guyatt GH, Sackett DL 1994)(see below).

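### The stated comparison leaves out patients who develop a non-AD dementia, which overstates PPV and may overstate specificity and LR+

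*Protocol*

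**What the plan says.** Section 3.1 sets the comparison of baseline characteristics "between the group progressing to AD after 2 and 3 years from diagnosis and the group remaining stable or reverting to a normal condition". Patients with another dementia belong to neither group: "The recruited MCI subjects progressing to a non-AD dementia shall be considered separately". The primary endpoint, in section 3.7 and in the Synopsis, says: "People with MCI who convert to other forms of dementia will be considered separately". The Synopsis design paragraph contrasts AD converters with non-converters at three years and then adds: "MCI subjects who will convert to other forms of dementia will be examined separately".

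Section 3.10 plans a contingency table for each biomarker, "processing parameters of sensitivity, specificity, positive predictive value and negative predictive value and overall accuracy", together with positive and negative likelihood ratios that are read against the bands of Table 6. It does not say which patients form the disease-negative column. After Table 5, section 3.9 refers to the "number of cases which convert and do not convert to" Alzheimer's dementia, which taken literally would count another dementia as non-conversion.

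Section 2 gives the purpose of the chosen diagnostic path: "in order to identify patients eligible to prescription of antidementia drugs which are currently under experimentation by RCTs".

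**The concern.** The group set aside is defined by what happens after the test. A clinician with a marker result at baseline cannot know which MCI patients will develop another dementia, so the test will be applied to them as well. A marker-positive patient who goes on to a non-AD dementia is a false positive for AD. Accuracy calculated without such patients describes a population that cannot be selected when the test is used.

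The measure most directly affected is PPV. The Synopsis states its target in the same terms: it wants new drugs reserved for MCI patients whose risk of conversion is 90% or more. Non-AD converters are to be expected, because entry in Table 1 of section 3.2 is open to a deficit in any cognitive domain and is not confined to memory.

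The choice between markers could also be affected. A marker that reacts to neurodegeneration in general gains more from the omission than one that is specific to AD, and telling these apart is part of the primary aim.

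**Working it through.** **The plan's own figures.** Table 2 in section 3.9 (FCSRT, 187 patients) reproduces: sensitivity 59/73 = 0.81, specificity 81/114 = 0.71, PPV 59/92 = 0.64, NPV 81/95 = 0.85.

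**Inputs from the protocol.** N = 400 and 40% AD conversion at three years (section 3.9). Sensitivity and specificity from section 1.2: FCSRT 0.81 and 0.71, MRI 0.60 and 0.75, CSF 0.71 and 0.77.

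**Assumptions.** The share s of the cohort that converts to a non-AD dementia and the marker positivity q in that group are not in the protocol. I use s = 10% and show q at 70% and 10%. I also take the quoted specificities to apply to stable or reverting patients; the protocol does not say so.

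**Formulas.** The cohort divides into 160 AD, 40 non-AD dementia and 200 stable or reverted.
- TP = 160 × Se; FP among stable or reverted = 200 × (1 − Sp); FP among non-AD dementia = 40 × q.
- Left out: specificity = Sp; PPV = TP / (TP + FP stable).
- Counted as AD-negative: specificity = 1 − (FP stable + FP non-AD) / 240; PPV = TP / (TP + FP stable + FP non-AD).
- LR+ = Se / (1 − specificity).

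**FCSRT.** TP = 129.6, FP stable = 58.
- Left out: PPV 129.6/187.6 = 0.691; specificity 0.71; LR+ 0.81/0.29 = 2.79.
- q = 70% (28 more false positives): PPV 129.6/215.6 = 0.601; specificity 1 − 86/240 = 0.642; LR+ 0.81/0.358 = 2.26.
- q = 10% (4 more): PPV 129.6/191.6 = 0.676; specificity 1 − 62/240 = 0.742; LR+ 0.81/0.258 = 3.14.

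**MRI.** TP = 96, FP stable = 50.
- Left out: PPV 96/146 = 0.658; specificity 0.75; LR+ 0.60/0.25 = 2.40.
- q = 70%: PPV 96/174 = 0.552; specificity 1 − 78/240 = 0.675; LR+ 0.60/0.325 = 1.85. In Table 6 this moves from the 2–5 band to the band below 2.
- q = 10%: PPV 96/150 = 0.640; specificity 1 − 54/240 = 0.775; LR+ 0.60/0.225 = 2.67.

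**Direction of the effect.** Adding 40q to the PPV denominator lowers PPV for every q above zero. Specificity and LR+ fall only if q exceeds 1 − Sp, which is 0.29 for FCSRT, 0.36 for EEG, 0.33 for PET, 0.25 for MRI, 0.23 for CSF and 0.34 for APOE4. At equality they do not change, and below it they rise.

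**Range.** For FCSRT, with s from 5% to 15% and q from 0.10 to 0.81, the overstatement of PPV runs from 0.7 points (0.670 vs 0.663) to 15 points (0.713 vs 0.563).

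**Comparison between markers.** Suppose CSF positivity in non-AD converters is 23%, as in stable patients. CSF PPV is 113.6/159.6 = 0.712 when they are left out and 113.6/168.8 = 0.673 when they are counted. With FCSRT at q = 70%, the CSF lead is 0.712 − 0.691 = 2 points in the first case and 0.673 − 0.601 = 7 points in the second.

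**The case against.** **Removal from the 2×2 tables is inferred.** Section 3.10 names no columns, separate consideration could mean a separately reported outcome class, and the sentence in section 3.9 can be read as keeping these patients among the negatives. This stands as a limit on certainty. It does not remove the point: section 3.1 names the comparison group without them, the Synopsis and section 3.7 repeat the separation, and nowhere is accuracy said to be calculated with them as AD-negative. At best the negative group is ambiguous.

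**A reader might infer that specificity and LR+ are necessarily inflated.** The protocol does not support that. The direction depends on positivity among non-AD converters, for which it gives no figure. Positivity above the threshold is plausible for memory tests, MRI, PET and EEG, but least assured for CSF and APOE4.

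**The worked figures rest on outside assumptions.** This is so. The exclusion of stroke history and of neuroimaging evidence of other causes may keep the non-AD share low. Table 2 simply divides 187 patients by AD status, so its 0.71 may already include other dementias.

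**A reader might also infer a further bias from drop-out**, because section 3.9 lists "death, severe neurodegenerative disease, dropout for poor compliance" as reasons for loss. That list explains a 20% sample-size allowance and is not a rule for removing patients from analysis. Extra PPV bias would need converters who leave to be counted while non-converters who leave are discarded, and the protocol never states such a pattern.

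**The sample size is not undermined.** The first calculation in section 3.9 tests sensitivity, which does not involve the disease-negative group.

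**Conclusion.** The point holds for PPV and conditionally for specificity and LR+. As the comparison is written, patients who develop another dementia fall outside both groups. A PPV calculated that way is too high for the intended use whenever any of them is marker-positive. In the 10% illustration the FCSRT overstatement is about 9 points at 70% positivity and about 1.5 points at 10%. Over the same two cases, counting these patients moves specificity from 0.71 down to 0.64 or up to 0.74. These sizes depend on an assumed non-AD share, an assumed positivity and the reading of the quoted specificities as stable-or-reverter values. The direction for PPV needs only one marker-positive patient in the group left out. That section 3.10 will apply the exclusion in its tables is the most natural reading of the protocol, but it is not stated there.

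**What to change.** In sections 3.1, 3.7 and 3.10, and in the matching Synopsis text, define the disease-negative group of the primary contingency tables as all patients without AD conversion by 36 months: stable, reverted, or with another dementia. Report the table restricted to stable and reverted patients as a secondary analysis, and describe the non-AD converters and their marker results separately as already intended. State that a patient who leaves the study with a diagnosed dementia is classified by that diagnosis. Bring the sentence after Table 5 in section 3.9 into line with this definition.

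The change needs analysis text only, with no additional patients, visits or tests. Its downside is a somewhat less favourable PPV and possibly a less favourable specificity.
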